1. INTRODUCTION

1.1 Study Overview

Almost 100,000 mastectomies are performed in the US to treat breast cancer each year.¹ Breast reconstruction represents a major advance in the care of breast cancer patients undergoing mastectomy and the use of immediate implant-based reconstruction is increasing.² However, many women with mastectomy are recommended to undergo radiation therapy to improve cancer outcomes.³ Radiation therapy currently entails over five weeks of daily treatment and can compromise outcomes of breast reconstruction. An alternative three-week short-course radiation regimen (hypofractionation) may improve reconstruction outcomes and be equally effective. The decision regarding conventional versus short-course radiation therapy after mastectomy and immediate reconstruction is relevant to approximately 20,000 women annually. Currently no information exists to help inform the treatment choice between conventional (long-course) versus hypofractionation (short-course) radiation therapy in women with mastectomy and immediate reconstruction.

Impact of radiation therapy after mastectomy on health of individuals and populations:

Mastectomy, or removal of the entire breast, is a common treatment strategy for breast cancer. In 2015, an estimated 231,840 new cases of invasive breast cancer were expected to be diagnosed in women in the US, including 60,290 new cases of non-invasive (in situ) cancer.⁴ Of these cases, almost 40 percent are treated with mastectomy.⁵ Patients with multicentric (involving more than one quadrant of the breast) cancers, cancers not easily encompassed by limited surgery such that an unacceptable cosmetic outcome would result, or patients at elevated risk for a new or recurrent breast cancer typically opt for mastectomy. In recent years, there has been an increase in the frequency of mastectomy perhaps due in part to patient preference and the wish to minimize new future breast cancer risk.¹ Radiation therapy is indicated for almost one-third of patients who receive mastectomy.³ After mastectomy, radiation is used to reduce the risk of breast cancer recurrence in the chest wall or regional lymph nodes. Radiation therapy has been established as standard treatment for patients with four or more positive (involved) axillary nodes, and there is increasing evidence that radiation improves outcomes in patients with one to three positive nodes. An update of the large meta-analysis of randomized trials showed a clear benefit to the use of post-mastectomy radiation therapy in patients with one to three positive axillary nodes, with respect to reducing local regional recurrence (recurrence in the breast area and nearby lymph nodes), overall recurrence, and deaths from breast cancer.⁶ After mastectomy, the main areas at risk for local-regional recurrence (and therefore, targeted in the planned radiation) are the nodal basins (axillary, supraclavicular, internal mammary) depending on anatomy, pathology, and extent of axillary surgery. Radiation techniques have continued to evolve to minimize long-term side effects.

Breast reconstruction and radiation therapy after mastectomy:

The option to receive breast reconstruction is a major advance for women undergoing mastectomy. Breast reconstruction has been shown to improve emotional, psychological, and physical well-being of women treated with mastectomy.^{7,8} Patient satisfaction after breast reconstructive surgery has been shown to be improved as well.⁹ Awareness of reconstruction as a routine issue to be addressed in the management of patients who require mastectomy^{10,11} and the use of implant-based reconstruction after mastectomy are increasing.²

Women who undergo mastectomy can receive immediate or delayed reconstruction. Breast reconstruction can begin at the time of mastectomy (“immediate”) as opposed to a separate, later operation (“delayed”). The psychological benefit of immediate reconstruction is established, clearly favoring immediate over delayed.¹² Immediate reconstruction also affords the plastic surgeon the opportunity to utilize more original breast skin, which may improve the ultimate cosmetic outcome. Delayed reconstruction may be preferable in settings where there is high-risk disease that requires an uncomplicated postoperative course in order to plan post-mastectomy radiation therapy, or if the technique and dose aspects of radiation are optimized by the absence of a reconstruction. The two main types of breast reconstruction are implant-based or autologous (patient tissue-based). Implant-based reconstruction typically consists of a tissue expander, which is a temporary, inflatable device placed under the pectoralis major muscle, that has a port or opening that permits the plastic surgeon to sequentially (over weeks to months) instill saline solution to create a breast mound. This process allows the body and skin to gradually adjust to the size of an implant. The tissue expander is eventually replaced with a permanent implant. Alternatively, in selected cases where the anatomy permits, a permanent implant may be placed directly under muscle and skin at the time of mastectomy. Implants are not expected to last a lifetime and may need to be replaced every 10-15 years.

Autologous tissue reconstruction utilizes a muscle-skin combination from another site (e.g., abdomen, back, buttock) or in some settings, can be performed without compromising muscle (using abdominal tissue anterior to the muscle). If post-mastectomy radiation therapy is delivered to an unreconstructed chest wall, delayed implant reconstruction usually is not possible or advisable given the long-term effects of radiation (tightness, scar tissue) on the chest wall and the accompanying inability to place a tissue expander or permanent implant under the irradiated pectoralis muscle and chest wall skin. There has been an increase in immediate implant-based reconstruction in recent years, particularly in patients who may require post-mastectomy radiation therapy. This trend is likely due in part to the ease of planning this type of surgery (shorter operative time, shorter recovery time). Moreover, immediate reconstruction allows for an implant option if radiation therapy will be delivered, as implant-based reconstruction is typically only possible prior to radiation—when the tissues of the chest wall are still pliable.

The combination of post-mastectomy radiation therapy and reconstruction is challenging. Radiation therapy can compromise the cosmetic outcome of the reconstruction and increase complications.^{13,14,15} Radiation is associated with an increased likelihood of forming scar tissue around the implant, resulting in long-term problems with increased hardness, suboptimal positioning (the implant can migrate on the chest wall), and the need to remove or replace the implant. There is also an increased risk of complications such as delayed healing and infection (sometimes requiring permanent removal of the implant). Women have reported less satisfaction with reconstruction in the setting of radiation therapy (versus no radiation).¹⁶

Patient and treatment characteristics have been evaluated in attempts to discern which may contribute to higher risk of complications or poor cosmetic outcomes. Factors described as being associated with poorer outcomes include age, medical conditions (e.g., smoking, high blood pressure, diabetes, body mass index), weight of breast specimen, and scar location.¹⁷⁻¹⁹ There is no agreement upon whether it is preferable to irradiate a tissue expander or a permanent implant.

Cordeiro et al. recently reported that six-year reconstruction failure rates were higher for irradiated tissue expanders compared to permanent implants, but initial tissue expander placement was associated with a higher proportion of good-to-excellent cosmetic results compared to an initial permanent implant.²⁰

Modification of the conventional radiation schedule may yield improved outcomes:

Hypofractionation, or short-course radiation therapy, reduces the number of radiation treatments and the overall treatment length, increasing patient convenience. This regimen has been shown in randomized trials (e.g., the START-B trial), largely in the breast-conservation setting, to reduce acute radiation therapy side-effects, decrease fatigue at six months and improve cosmetic results.^{21,22} A large randomized study from Canada showed a hypofractionated regimen to be safe and effective in early-stage breast cancer.²³ Despite these results, adoption of hypofractionation was initially sluggish in the breast-conserving therapy setting^{24,25} likely due to a preference for the familiarity and experience with conventional long-course radiation therapy. Of note, patients receiving care in community practice are less likely to receive hypofractionation²⁶ perhaps due to increased financial incentives to treat with longer-course radiation therapy. The majority of patients in the START-B trial, and all of the patients in the Canadian trial, were treated solely to the whole breast, without a separate radiation field to treat lymph nodes. In the post-mastectomy setting, patients routinely have lymph node radiation. Some of the radiation side effects associated with this separate lymph node field include lymphedema (potentially related to the extent of surgery), and, much less likely, radiation pneumonitis (inflammation of the lung due to radiation—typically temporary and treatable), and, extremely rarely, brachial plexopathy (injury to the nerves that supply the arm). Long term data following hypofractionation to the lymph nodes have not revealed an increased risk of brachial plexopathy.²⁷ While hypofractionation is used commonly in the UK in the post-mastectomy setting, there are no randomized studies specifically studying outcomes following its use in women who undergo breast reconstruction. Therefore, there is an even greater barrier to the use of hypofractionation in this setting in the US. With improved cosmetic results found with hypofractionation in the breast conservation setting, this shorter regimen may have the potential to improve reconstruction success rates (which are modest overall) for patients who require post-mastectomy radiation. In addition, given the financial repercussions of a reduced number of radiation treatments, high-quality, Level I randomized evidence is needed in this population to change practice patterns regarding the radiation regimen.

Gaps in Evidence:

Mastectomy, immediate implant-based reconstruction, and radiation therapy constitute a common treatment paradigm. There are conflicting data on the treatment outcomes with respect to quality of life (QoL), cosmetic results, and complications. Variability in treatment technique (surgery and radiation) contributes to the uncertainty, and in the absence of prospective data with specified treatment protocols and rigorous evaluation of outcomes, this uncertainty is likely to continue. Hypofractionated radiation has been studied well in breast-conserving therapy, with equivalent efficacy in preventing cancer recurrence, and a possible benefit in cosmetic outcome, when compared to conventional, longer- course radiation. There are limited data on its use in the post-mastectomy setting and with nodal irradiation.

1.2 Rationale

Over 180,000 diagnoses of invasive breast cancer are made in the US each year. Over one-third of women with early stage and over half with late-stage breast cancer are treated with mastectomy (removal of the entire breast) due to tumor size, multiple cancers within the breast, genetic cancer predisposition, and/or patient preference. Following treatment with mastectomy, women who receive breast reconstructive surgery may experience better quality of life as they do not have to leave surgery with a bare chest wall. However, large randomized trials of post-mastectomy radiation therapy reveal a survival benefit with the addition of radiation after mastectomy in women who have cancer present in the axillary lymph nodes.⁶ The delivery of radiation therapy in the presence of a breast reconstruction is challenging and often leads to undesirable consequences including reconstruction loss, need for major surgical revision, or poor cosmetic outcomes. Therefore, oncologists and patients are forced to decide between the potential for improved oncologic outcomes with radiation therapy versus increased likelihood of complications and suboptimal cosmetic results. Because of this, some patients may be foregoing reconstruction if radiation therapy after mastectomy is needed; or foregoing radiation therapy if they have had breast reconstructive surgery.²⁸

Hypofractionation enhances patient convenience and decreases treatment burden. This regimen has been shown in randomized trials largely in the breast-conservation setting to reduce acute radiation therapy side-effects, decrease fatigue at six months and improve cosmetic results.^{21,22} Despite these results, adoption of hypofractionation has been slow among women with breast cancer treated with breast-conserving surgery^{24,25} likely due to familiarity and experience of conventional long-course radiation therapy. While hypofractionation is used commonly in the UK for patients with mastectomy, there are no randomized studies particularly studying outcomes following shorter course radiation therapy in women who undergo mastectomy with breast reconstruction. Therefore, there is an even greater barrier to the use of hypofractionation in this setting in the US. With improved cosmetic results found with hypofractionation, this shorter regimen may have the potential to improve reconstruction success rates which are unfortunately modest overall, for patients who require post-mastectomy radiation. Especially in contrast to financial disincentives to reduce number of radiation treatments, Level I randomized evidence is needed in this population to change practice patterns regarding radiation regimen.

Patient-centeredness:

Our study of radiation fractionation regimens has the potential to increase use of hypofractionation among women treated with mastectomy, thereby decreasing treatment burden. Our team of patient stakeholders ensures that our outcomes measures encompass all domains of survivorship after breast cancer (physical and mental health as well as satisfaction with the decision-making process). Despite the large numbers of breast cancer survivors who undergo mastectomy, reconstruction and radiation therapy, little is known about which domains of quality of life are affected and their importance to these patients. This study uses previously validated tools for measuring patient outcomes, and have added questions for areas which are important to patients that may not have been captured adequately by previous tools. In concert with the increasing awareness of the importance of survivorship care to cancer care, identifying a comprehensive set of outcomes measurement tools following treatment with radiation therapy, mastectomy, and reconstruction is an important asset for future treatment evaluation in these women. In summary, the proposed pragmatic trial is *highly significant* because:

1. A critical knowledge gap exists for a common medical condition in a well-defined population
2. Patients and/or their physicians may be foregoing radiation to preserve the cosmetic results of reconstruction
3. Clinicians are unsure whether to adopt hypofractionation or continue with the familiar but problematic conventional treatment
4. Hypofractionation has the potential to improve outcomes following breast reconstruction
5. Hypofractionation decreases treatment burden for patients with fewer radiation treatments
6. There are no randomized studies specifically evaluating hypofractionation after mastectomy and reconstruction
7. The trial is being conducted in diverse settings including community oncology practices
8. Engaged patient partners will help disseminate findings
9. The trial will examine outcomes that matter to patients including the QoL and cosmetic results
10. The trial will have long-term implications for improving and measuring the QoL of breast cancer survivors and will enhance the increasingly important field of survivorship research.

2. OBJECTIVES

2.1 Study Design

The FABREC study is a pragmatic randomized trial of hypofractionation versus conventional radiation therapy in women who have undergone mastectomy and immediate breast reconstruction.

The trial will be conducted at academic and community practice sites to ensure a diverse and representative patient population. Study participants will be randomized 1:1 to conventional fractionation or hypofractionation after mastectomy and breast reconstruction with a tissue expander or implant.

All participants will be assessed for cosmetic and reconstruction outcomes, lymphedema and cancer status through month 18. During the 10-year follow-up period, participants will be assessed for oncologic outcomes (local recurrence, distant disease, and survival) and side effects. Surveys will be used to ask participants to report pain, appearance, mobility, and self-image.

2.2 Objectives

Objective 1: Compare the effect of short-course versus long-course post-mastectomy radiation therapy on highly-relevant patient-reported outcomes (PROs) and outcomes prioritized by individual trial participants.

Our primary outcome is the Physical Well Being (PWB) domain of the FACT-B instrument. PRO assessment will be further patient-focused, as we will also ask each subject to choose the FACT-B subdomain most relevant to their experience and separately correlate this domain to that patient's radiation schedule. We will thereby create a more

patient-centered outcome by comparing short- versus long-course radiation according to the subscale selected to be most important to the individual patient. In addition, we will assess pain, arm mobility, lymphedema, self-image, satisfaction with decision to undergo reconstruction, sexual well-being, functional well-being, and treatment burden in all patients using standard instruments.

Hypothesis: Short-course radiation therapy will improve patient quality of life in multiple domains.

Objective 2: Compare clinical outcomes for patients receiving short-course versus long-course radiation.

These include complications and clinically-assessed cosmetic results. We will also create an infrastructure to monitor long term oncologic outcomes such as recurrence and breast-cancer specific survival, and rare radiation side effects (secondary malignancy and brachial plexopathy).

Hypothesis: Short-course radiation therapy will decrease complications, improve clinician-quantified cosmetic results, and will have no increased risk of local or regional recurrence or side-effects.

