The primary analysis and power: We hypothesize that hypofractionated (short-course) radiation therapy has a higher reconstruction success rate, compared to the conventional fractionation (long-course) radiation at 18-months. We will use Chi-square test for 2x2 table to test this superiority hypothesis. We will also construct a two-sided 95% confidence interval for the difference in the composite outcome of reconstruction success likelihood (defined as no major complications, presence of reconstruction, and good or excellent cosmetic outcome). Recent estimates of reconstruction success after implant reconstruction and conventional radiation reveal a 71% likelihood at the 2-year time period.⁴⁶ “**Table: Effect size and power for superiority tests**” shows the available power with various reconstruction success probabilities for hypofractionation (short-course treatment), given the sample size of 400 patients. Variables that may affect outcomes such as chemotherapy regimen, endocrine therapy and patient age will be assessed for impact to ensure balance between both treatment arms.

Table: Effect size and power for superiority tests		
Reconstruction Success Likelihood (%)		Power (%)
Long-course radiation	Short-course radiation	
71.0	82.8	80
71.0	84.4	90

N=400 randomized patients and α (two-sided)=0.05

[figure not shown]
Data monitoring of local/regional recurrence event:

We will also follow oncologic outcomes to exclude any unexpected increase in the risk of recurrence with hypofractionation (short-course) radiation therapy, although a detectable increase in recurrence rates is unlikely given data from prior experiences of hypofractionation. The cumulative incidence of local or regional recurrence in a recent series of post-mastectomy

radiation therapy is about 2% at 18 months.³ Therefore, in the case where the recurrence rate is suggested to be statistically significantly greater than 2%, the study will be suspended to allow for investigation.

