Local/regional recurrence event rate monitoring will occur at the first meeting of the DF/HCC Data and Safety Monitoring Board (DSMB) and continue until the last patient has completed radiation. Data analysis will be performed every 6 months (see Section 11). Specifically, the event rate and corresponding 0.95 exact binomial confidence interval will be calculated, where the numerator is the number of the local/regional recurrence events and the denominator is the number of patients who have completed short-course treatment at time of analysis. The results will be reviewed by the DSMB. If the lower boundary of the 0.95 confidence interval is greater than 2%, accrual of the study will be suspended and a decision will be made as to whether accrual can be resumed or if the study should be closed by the study team in consultation with the DSMB, IRB and study advisory board. The boundary for this criterion is shown in “**Figure: Stopping boundary for local/regional recurrence-event monitoring**”. With the sample size of 200 in the short-course radiation arm, the probability that the interim data meet the stopping criteria (see figure) in the course of the trial is 72% if the true local or regional recurrence rate were 5%. It would be 98% if the true recurrence rate is 8% at 18-months.

Figure: Stopping boundary for local/regional recurrence-event monitoring

There has been no suggestion of increased rare radiation side-effects or mortality with hypofractionation (short-course) radiation therapy with long term follow up in the studies using hypofractionation.^{23,24,31} Therefore, we do not expect any increased risk of side-effects in our short-course arm. Nevertheless, to be extra cautious, we will follow these outcomes in our patients. We recognize that our study is too short to detect differences in long-term distant recurrence, cardiac mortality and overall mortality. Therefore, we will create an infrastructure with which monitor these outcomes and apply for additional funding for longer follow up.

10e. Heterogeneity in treatment (HTE) outcomes

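### Objective 2 hypothesises no increase in local or regional recurrence with short-course radiation, but the plan specifies no dedicated between-arm estimate of recurrence

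*Combined protocol and SAP*

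**What the plan says.** Section 2.2 sets Objective 2 as "Compare clinical outcomes for patients receiving short-course versus long-course radiation". It lists complications and cosmetic results as the compared outcomes, then adds: "We will also create an infrastructure to monitor long term oncologic outcomes such as recurrence and breast-cancer specific survival". The hypothesis that follows includes the expectation that short-course "will have no increased risk of local or regional recurrence or side-effects". No margin is given there or elsewhere.

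Section 10c is the analysis plan for clinical and oncologic outcomes. It states the purpose of following recurrence: "We will also follow oncologic outcomes to exclude any unexpected increase in the risk of recurrence with hypofractionation". The reference is an outside series in which the cumulative incidence after post-mastectomy "radiation therapy is about 2% at 18 months". Every 6 months an event rate is calculated in which "the denominator is the number of patients who have completed short-course treatment at time of analysis". The rule is: "If the lower boundary of the 0.95 confidence interval is greater than 2%, accrual of the study will be suspended". Looks end when the last patient has finished radiation. The plan gives the probability of crossing, with 200 short-course patients, as 72% at a true rate of 5% and 98% at 8%.

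Three other places bear on the point. Section 7.2 makes local/regional recurrence a reportable serious event for 3 years from the start of radiation, in both arms. Section 10f compares adverse events between arms by Fisher's exact test, by seriousness, grade and attribution. Section 11.1 lists the local/regional recurrence rate among items the Data and Safety Monitoring Board (DSMB) may receive.

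**The concern.** The hypothesis is about short-course relative to long-course. The specified analysis concerns one arm relative to a fixed outside figure. The two can disagree in both directions. If this population recurs at more than 2% under either schedule, the rule can trigger with no excess from short-course. If short-course is worse than long-course, the rule may stay silent. The denominator is also short-course completers rather than patients randomised to short-course, although section 6.6 permits a switch from short-course to standard fractionation and section 10b adopts intention-to-treat for the primary endpoint.

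The trial is meant to inform a change of practice, so the final report will need to say something about recurrence. As written, the plan gives the authors no prespecified between-arm difference to report and no statement of how precise it would be.

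**Working it through.** **1. Reproduce the plan's figures.** Inputs: 200 short-course patients, a 95% exact interval, a threshold of 2% and looks every 6 months (section 10c); accrual over 21-27 months (section 10a), hence about 4-5 looks. The exact lower limit for x events in n patients is the 0.025 quantile of Beta(x, n − x + 1). The smallest x that puts it above 0.02 is 4 of 50, 6 of 100, 8 of 150 and 9 of 200. Crossing probabilities by exact binomial recursion over equally spaced looks, with every outcome known at the look:

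| True short-course rate | 4 looks | 5 looks | Plan |
|---|---|---|---|
| 5% | 71.3% | 72.1% | 72% |
| 8% | 98.5% | 98.6% | 98% |

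The plan's figures reproduce, so this is the rule intended.

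**2. Ask what the rule says about a difference.** The long-course rate is not an input, so the crossing probability is the same whatever that rate is. With outcomes known at once, the rule triggers in about 20% of trials at a true short-course rate of 3% and in 46-47% at 4%. The 4% figure covers two opposite situations:

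- Both arms at 4%, true difference zero: suspension in 46-47% of trials.
- Long-course 2% and short-course 4%, a doubling: silence in 53-54% of trials (100 − 47 and 100 − 46).

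**3. Allow for limited follow-up.** The 2% is an 18-month figure, but the denominator takes in patients who have only just finished radiation, and looks end when the last patient finishes. Assumptions: constant hazard λ = −ln(1 − p)/18 per month (0.00169 at p = 3%, 0.00227 at p = 4%), uniform accrual over 21-27 months, radiation starting 0-4 months after randomisation (section 5.2 sets the maximum), and looks every 6 months plus one when the last patient completes radiation. By simulation the trigger probability falls to about 3-7% at 3% and 11-25% at 4%; the range is over the accrual period. A doubling from 2% to 4% then passes silently in about 75-89% of trials.

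**4. What a between-arm estimate would give.** Take 2% in each arm, 4 of 200 against 4 of 200.

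- Wald: SE = √(2 × 0.02 × 0.98 / 200) = 0.0140; half-width 1.96 × 0.0140 = 0.027, or ±2.7 points.
- Newcombe: Wilson limits for 4/200 are 0.0078 and 0.0503; half-width √[(0.0503 − 0.02)² + (0.02 − 0.0078)²] = 0.0327, or ±3.3 points.

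The Newcombe upper limit corresponds to 2% + 3.3% = 5.3%, more than double the reference risk. Non-inferiority power, Φ(margin/0.0140 − 1.96), is 30% for a 2-point margin and 82% for a 4-point margin. Both margins are illustrative, since the plan states none.

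**5. Does section 10f fill the gap?** Recurrence may enter the Fisher comparison as a reportable serious event. Section 7.2 notes that it is not a CTCAE term, so grading does not isolate it, and 10f does not name it. Fisher's test gives a p-value, not a difference with a CI.

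**The case against.** The strongest reply is that recurrence is only being monitored. Section 2.2 speaks of an infrastructure for long-term oncologic outcomes, the 2% rule sits under a data-monitoring heading, and a trigger against a fixed rate is a legitimate safety device. The last part stands, and the rule should stay. The rest does not remove the mismatch: section 2.2 still states the hypothesis, section 10c gives the purpose as excluding an increase, and its caveat that the study is too short names distant recurrence, cardiac mortality and overall mortality, not local/regional recurrence.

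A second reply is that an added comparison would be too imprecise to settle the question. That is true for small margins (step 4). It is a reason to state the precision and soften the claim, not to leave the comparison out.

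Three stronger readings are tempting and are not supported:

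- *That the trial will never estimate the difference.* Recurrence is collected in both arms, 10f may count it, and 11.1 does not limit the board's recurrence rate to one arm. What is missing is a dedicated, prespecified estimate.
- *That the rule would wrongly suspend accrual in a fifth to nearly half of trials if both arms recur at 3-4%.* Those figures need every outcome to be known at once, which the accrual and follow-up timeline does not allow. Nor does crossing close the study: accrual is suspended while the study team decides with the DSMB, IRB and advisory board.
- *That the plan treats a silent rule as proof of no increase.* It nowhere says so. The risk is only that a reader could take it that way.

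**Conclusion.** The concern holds as a gap in the analysis plan, not as an arithmetic error. A comparative hypothesis on local/regional recurrence is left with a one-arm rule that cannot address it and an adverse-event comparison that does not isolate it. The rule triggers with probability about 20% and 46-47% at true short-course rates of 3% and 4% under instant outcomes, and about 3-7% and 11-25% under the follow-up assumptions in step 3, so silence says little about an increase. The second pair depends on the assumed constant hazard, uniform accrual and delay to radiation. The precision of ±3.3 points (±2.7 by Wald) assumes 2% in both arms and 200 evaluable patients per arm. Neither the primary quality-of-life endpoint nor the reconstruction-success comparison is affected. The change is worth making because the data are already being collected.

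**What to change.** 1. Keep the 2% trigger in section 10c, labelled as a safety rule that does not test the Objective 2 hypothesis.
2. In each DSMB report, show the concurrent long-course rate and the between-arm difference with a 95% CI.
3. In the final analysis, prespecify the difference in 18-month cumulative incidence of local/regional recurrence by randomised arm (intention-to-treat) with a 95% CI. State how deaths and distant recurrences are handled, since section 7.2 ends follow-up at distant recurrence.
4. Reword the recurrence part of the Objective 2 hypothesis as estimation, give the expected precision (about ±3.3 points by Newcombe, ±2.7 by Wald, at 2% with 200 per arm), and make no claim of no increased risk.

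The cost is a weaker stated claim, edits to the objective and the analysis plan, and one extra table from data already collected.
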